### 2.3.2. Benefit Assessment

PF-07304814 will not provide any clinical benefit to healthy participants. The purpose of the study is to characterize mass balance and further the understanding of human metabolism of [C] PF-07304814.

### 2.3.3. Overall Benefit/Risk Conclusion

PF-07304814 will not provide any clinical benefit to healthy participants in this study. Taking into account the measures taken to minimize risk to participants of this study, the potential risks identified in association with administration of PF-07304814 are justified by the anticipated benefit, in terms of contribution to the process of developing new therapy in an area of unmet medical need.

## 3. OBJECTIVES AND ENDPOINTS

Objectives	Endpoints
Primary:	Primary:

To confirm mass balance and characterize the routes of elimination of [C]-PF-07304814 and drug related materials following 420 nCi/500 mg dose of [C] PF-07304814

To evaluate the PK of PF-07304814 and PF-00835231 in plasma and characterize the PK of total [C] in plasma

	

Amount of [C] recovered in urine and feces, as a percent of the total [C] dose administered

Plasma PK parameters, including AUClast, AUCinf, Cmax, Tmax, C24, CL, Vss, and t1/2

Total [C] in plasma and PK of PF-07304814 and PF-00835231 in plasma

Secondary Objective:	Secondary:

To identify metabolites of PF-07304814 in plasma, urine and feces, if possible

To evaluate the safety and tolerability of a single, 24-hour constant-rate, continuous infusion of 500 mg PF-07304814 containing 420 nCi [C]-PF-07304814 in healthy participants

	

Identification and determination of relative abundance of the metabolites of PF-07304814 in plasma, urine, and feces

Assessment of TEAEs, clinical laboratory abnormalities, vital signs, physical exam, and 12-lead ECGs.

## 4. STUDY DESIGN

### 4.1. Overall Design

This is a Phase 1, open-label, single-dose, single-center study to characterize mass balance and further the understanding of human PK, metabolism, and excretion of [C] PF-07304814. The study will be conducted in approximately 5 healthy participants. Each participant will receive a single, 24-hour constant-rate, continuous IV infusion of 500 mg PF-07304814 containing approximately 420 nCi [C] PF-07304814.

Approximately 5 participants will be enrolled. Each participant will be screened to determine eligibility within 42 days prior to dosing to confirm that they meet the inclusion and not the exclusion criteria specified in [Section 5.1](#) and [Section 5.2](#), respectively. Medical history and results of physical examination, physical measurements, vital signs, 12-lead ECGs, and clinical laboratory evaluations will determine eligibility. Participants will be admitted to the CRU on Day -1 and remain in the CRU through Day 10. Participants will be discharged on Day 10 following the final assessments. Participants who withdraw will not be replaced unless the number of completed participants falls below 4. Refer to [Figure 1](#) for details.

On Day 1, each participant will receive a single, 24-hour constant-rate, continuous IV infusion of 500 mg PF-07304814 containing approximately 420 nCi [C] PF-07304814. Serial blood samples will be collected at specified times (see [SoA](#) for details) up to 216 hours post the start of the infusion. Total urine collections will be made just before dosing (“blank”) and at 24-hour intervals until the end of the study. Feces will be collected from Day -1 (“blank”), and at the time of passing while the participant is confined in the clinic. Daily sample collections will continue through the morning of discharge. Participants will be confined from at least 24 hours prior to dosing on Day 1 until at least the morning of Day 10 (216 hours) post infusion start.

Complete physical examinations, BP, pulse rate, oral temperature, ECGs, and safety laboratory tests will be conducted, and AEs and concomitant medications will be monitored throughout the study to assess safety. Before the participant is released, a complete physical examination will be conducted along with safety labs, ECG, BP, heart rate and oral temperature.

A safety follow-up call will be made to participants approximately 28 to 35 days from administration of the dose of study intervention.

The total planned duration of participation, from the Screening visit to the last Follow-up phone call, is approximately up to 11 weeks.

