### Rationale

This open-label, single-dose study in approximately 5 healthy male and female (of non-childbearing potential only) participants has been designed to characterize mass balance and further the understanding of human pharmacokinetics, metabolism, and excretion of PF-07304814 administered at a dose of 500 mg [C] PF-07304814 containing approximately 420 nCi [C] PF-07304814 as a constant-rate, continuous IV infusion over 24 hours. The sample size of approximately 5 was selected to ensure at least 4 fully evaluable participants with completed collections of plasma, urine, and fecal samples. This is a standard sample size used for mass-balance/ADME studies which include assessment of metabolic profiling and is not based on empirical data or hypothesis testing criteria.

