## **4.2. Scientific Rationale for Study Design**

This study is a Phase 1 open-label, single-dose study in healthy males and females of non-childbearing potential, designed to characterize mass balance and investigate the PK, metabolism, and excretion of [C] PF-07304814, characterize plasma, fecal, and urinary [C] and identify any metabolites, if possible. The knowledge of the metabolism and routes of elimination of PF-07304814, PF-00835231 (active moiety), and associated metabolites is useful for evaluating the likelihood of effects of renal or hepatic impairment on the overall disposition.

The sample size of approximately 5 was selected to ensure at least 4 fully evaluable participants with completed collections of plasma, urine, and fecal samples.

Knowledge gained in this study will help guide study designs to address potential drug interactions and special population studies.

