### **9.2. Analysis Sets**

For purposes of analysis, the following analysis sets are defined:

Participant Analysis Set	Description
Enrolled/Randomly assigned to study intervention	"Enrolled" means a participant's, or their legally authorized representative's, agreement to participate in a clinical study following completion of the informed consent process and screening. Potential participants who are screened for the purpose of determining eligibility for the study, but do not participate in the study, are not considered enrolled, unless otherwise specified by the protocol. A participant will be considered enrolled if the informed consent is not withdrawn prior to participating in any study activity after screening.
Full Analysis Set (FAS)	Example: All participants assigned to study intervention and who take study intervention.
Safety Analysis Set	All participants assigned to study intervention and who take at least 1 dose of study intervention.
PK Concentration Analysis Set	The PK concentration analysis set for PF-07304814 is defined as all participants who receive study intervention and have at least one measurable PF-07304814 and PF-00835231 concentration. The PK concentration analysis set for [  C] is defined as all participants who receive study intervention and have at least one [  C] measurement.

Participant Analysis Set	Description
Mass Balance Analysis Set	All participants who receive study intervention and who have evaluable total [  C] concentration (urinary and fecal) data and who had no protocol deviations or AEs (such as diarrhea or severe constipation) that may have affected the mass balance analysis.

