### **9.5. Sample Size Determination**

A sample size of 4 participants is considered the minimum sample size for mass-balance/ADME studies which include assessment of metabolic profiling. The sample size is not based on empirical data or hypothesis testing criteria. Approximately 5 participants will be enrolled to study intervention such that approximately 4 evaluable participants complete the study with completed collections of plasma, urine, and fecal samples.

If the number of fully evaluable participants falls below 4, participants may be replaced.

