5.6.2. Deviations Assessed Post-Randomization

A full list of protocol deviations for the study report will be compiled prior to database closure. Any significant deviation from the protocol will be reviewed prior to database closure and a decision taken regarding evaluation for each analysis population.

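### Do the two replacement rules (fewer than 4 completed in Section 4.1, fewer than 4 fully evaluable in Section 9.5) leave the minimum of 4 unprotected?

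*Protocol*

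**What the plan says.** The protocol plans to enrol approximately 5 participants. Section 9.5 states that "A sample size of 4 participants is considered the minimum sample size for mass-balance/ADME studies" and plans enrolment "such that approximately 4 evaluable participants complete the study". The synopsis gives the reason for about 5 as "to ensure at least 4 fully evaluable participants with completed collections of plasma, urine, and fecal samples", and Section 4.2 repeats it: "The sample size of approximately 5 was selected to ensure at least 4 fully evaluable participants".

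Two sentences govern replacement:

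- Section 4.1: "Participants who withdraw will not be replaced unless the number of completed participants falls below 4".
- Section 9.5: "If the number of fully evaluable participants falls below 4, participants may be replaced".

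Section 4.4 defines completion by finishing all study periods up to the last visit or scheduled procedure, with no condition on samples. The Mass Balance Analysis Set (Protocol 9.2, SAP 5.1.2) is narrower. It needs evaluable urinary and fecal carbon-14 data from participants "who had no protocol deviations or AEs (such as diarrhea or severe constipation) that may have affected the mass balance analysis". The SAP has no replacement rule. On evaluability, SAP 5.6.2 says: "Any significant deviation from the protocol will be reviewed prior to database closure and a decision taken regarding evaluation for each analysis population".

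**The concern.** The two sections count different people. Someone with diarrhea that compromised the fecal collection could be a completer under 4.4 and yet fall outside the Mass Balance Analysis Set. If one of five withdraws and one of the four completers is not evaluable, three are left. Section 4.1 read alone then says the withdrawal is not replaced, because four completed, while Section 9.5 says replacement is allowed. The primary recovery endpoint could rest on fewer participants than the protocol's own minimum, depending on which page the site consulted.

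Three further points add to the impression:

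- Neither sentence makes replacement compulsory, although the synopsis and 4.2 speak of ensuring four.
- *Fully evaluable* is described by completed collections and is not tied to the Mass Balance Analysis Set.
- No time is given for making the 9.5 count. The SAP places the decision on analysis populations before database closure, which might be too late to enrol anyone.

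**Working it through.** **Is there a figure to reproduce?** No. Section 9.5 says that the sample size does not rest on empirical data or hypothesis testing, and no loss rate is given. One spare participant is a reasonable allowance: 5 × (1 − d) is at least 4 for any overall loss rate d up to 20%. The chance of at least 4 evaluable out of 5 with no replacement is (1 − d)^5 + 5d(1 − d)^4, which is 97.7% at d = 5%, 91.9% at 10% and 73.7% at 20%. These values of d are assumptions.

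**Do the two rules ever block four?** Let C be the number of completers out of 5 and E the number evaluable, with E below 4.

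| Completers | Section 4.1 | Section 9.5 | Can four be reached? |
|---|---|---|---|
| C = 5 | Silent, since nobody withdrew | Permits replacement | Yes |
| C = 4 | The one withdrawal is not replaced | Permits replacement | Yes, see below |
| C ≤ 3 | Replacement not barred | Permits replacement | Yes |

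Only C = 4 needs thought. Suppose k of the four completers are not evaluable, with k at least 1, so that E = 4 − k. Section 4.1 is about participants who withdraw, and the k completers did not. Replacing them under 9.5 with evaluable participants gives (4 − k) + k = 4. The withdrawn participant is never replaced, so 4.1 is respected. If a replacement also proves non-evaluable, the 9.5 count is still below 4 and its permission still applies.

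**How often would C = 4 with E ≤ 3 arise?** Assume independent losses, with withdrawal probability w and probability q that a completer is not evaluable:

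P(C = 4, E ≤ 3) = 5w(1 − w)^4 × [1 − (1 − q)^4]

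| w | q | First factor | Second factor | Result |
|---|---|---|---|---|
| 2% | 2% | 0.0922 | 0.0776 | 0.7% |
| 5% | 5% | 0.2036 | 0.1855 | 3.8% |
| 10% | 5% | 0.3281 | 0.1855 | 6.1% |
| 5% | 10% | 0.2036 | 0.3439 | 7.0% |
| 10% | 10% | 0.3281 | 0.3439 | 11.3% |

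The result is zero if either rate is zero. At 10%/10% the chance of fewer than four evaluable before any replacement is 24.2%: 11.3% with C = 4, 4.8% with C = 5 and 8.1% with C ≤ 3. Section 9.5 permits replacement in all three parts. The 24.2% therefore describes five participants with no replacement at all; it is not the cost of the wording.

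**Are the assumed rates plausible?** The documents cannot settle this. The nearest evidence is the earlier healthy-participant study of the same 24-hour infusion, which had no discontinuations due to adverse events (Section 2.2.4.1; other reasons are not reported there). The design also works against non-evaluability. Participants are confined through Day 10 (4.1), people with irregular bowel habit are excluded (5.2, criterion 22), fiber and laxative provisions apply (5.3.1), and all diarrheal material is kept for possible carbon-14 analysis (8.4.3). The analysis-set exclusion applies only where an event may have affected mass balance, not to every episode.

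**Would a single trigger change anything?** A common rule that participants may be replaced when fewer than four are fully evaluable is Section 9.5 restated. It allows the same actions in every row of the first table and guarantees four no better.

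**The case for a change.** The strongest reply is that calling the extra participant a replacement for the completer, and not for the withdrawal, is a technicality. A coordinator who opens only 4.1 may take four completers as sufficient and stop. Section 4.4 shows that completion and evaluability really are different, and the protocol itself foresees diarrhea and constipation. Discretionary wording cannot ensure anything, and a count with no stated time may be made too late.

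Part of this stands. The terms differ, *at least 4* sits beside *approximately 4*, and both could be tidied whenever the text is next edited. It is also true that only compulsory replacement would secure four by construction. That would remove the sponsor's discretion over exposing a further healthy volunteer, who gains no clinical benefit (2.3), in a descriptive study. Keeping the discretion is a fair trade-off.

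The rest does not carry far. *Fully evaluable* is described, through completed plasma, urine and fecal collections, and reading it together with the Mass Balance Analysis Set is what an analyst would do anyway. SAP 5.6.2 sets a latest point for assigning analysis populations and does not forbid an earlier look. This is a single-center, open-label study in which the sponsor may review data as it proceeds (Protocol 9.4, SAP 3), so evaluability can be judged as each participant's collections end.

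**Conclusion.** The concern does not call for a change. The two sentences are worded differently but can be obeyed together: 4.1 limits only the replacement of withdrawals, and 9.5 allows replacement whenever fewer than four are fully evaluable. Reaching four is blocked in none of the possible patterns of loss. The 3.8% to 11.3% depends on assumed, independent loss rates of 5% to 10%, falls to 0.7% at 2%, and is not the probability of a real obstruction. A harmonized trigger that kept discretion would alter no permitted action, and the study tests no hypothesis, so no estimate or conclusion depends on the wording. What remains is a clerical mismatch of terms and some unstated detail on definition and timing that the sponsor and analysts can fill sensibly. This conclusion rests on reading 4.1 and 9.5 together and on taking the restriction in 4.1 to mean what it says, namely participants who withdraw.

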## **4.2. Scientific Rationale for Study Design**

This study is a Phase 1 open-label, single-dose study in healthy males and females of non-childbearing potential, designed to characterize mass balance and investigate the PK, metabolism, and excretion of [C] PF-07304814, characterize plasma, fecal, and urinary [C] and identify any metabolites, if possible. The knowledge of the metabolism and routes of elimination of PF-07304814, PF-00835231 (active moiety), and associated metabolites is useful for evaluating the likelihood of effects of renal or hepatic impairment on the overall disposition.

The sample size of approximately 5 was selected to ensure at least 4 fully evaluable participants with completed collections of plasma, urine, and fecal samples.

Knowledge gained in this study will help guide study designs to address potential drug interactions and special population studies.

### **4.2.1. Choice of Contraception/Barrier Requirements**

Human reproductive safety data are not available for PF-07304814, but there is no suspicion of human teratogenicity based on the intended pharmacology of the compound. Therefore, the use of a highly effective method of contraception is required (see [Section 10.4](#)).

### **4.2.2. Collection of Retained Research Samples**

Retained Research Samples will be collected and stored for further analyses which may, for example, provide greater understanding of the study intervention.

## **4.3. Justification for Dose**

The total drug dose of 500 mg PF-07304814 selected for this study is within the anticipated clinically relevant dose range. This dose is below the highest dose evaluated in healthy participants (700 mg IV administered over 24 hours), which was safe and well tolerated. A dose of 500 mg PF-07304814 is expected to result in exposures below those observed following a single, 24-hour constant-rate, continuous IV infusion in healthy participants.

## **4.4. End of Study Definition**

The end of the study is defined as the date of the last visit of the last participant in the study or last scheduled procedure shown in the [SoA](#) for the last participant in the trial.

A participant is considered to have completed the study if he/she has completed all periods of the study, including the last visit or the last scheduled procedure shown in the [SoA](#).

## 5. STUDY POPULATION

This study can fulfill its objectives only if appropriate participants are enrolled. The following eligibility criteria are designed to select participants for whom participation in the study is considered appropriate. All relevant medical and nonmedical conditions should be taken into consideration when deciding whether a particular participant is suitable for this protocol.

Prospective approval of protocol deviations to recruitment and enrollment criteria, also known as protocol waivers or exemptions, is not permitted.

### 5.1. Inclusion Criteria

Participants are eligible to be included in the study only if all of the following criteria apply:

#### Age and Sex:

1. Male and female participants must be 18 to 55 years of age, inclusive, at the time of signing the ICD.
  - Women must be of non-childbearing potential: must meet the criteria for WNOCBP outlined in [Section 10.4.3](#).
  - Refer to [Appendix 4](#) for reproductive criteria for male ([Section 10.4.1](#)) and female ([Section 10.4.2](#)) participants.

#### Type of Participant and Disease Characteristics:

2. Participants who are overtly healthy as determined by medical evaluation including medical history, physical examination, laboratory tests, and ECGs.
3. Participants who are willing and able to comply with all scheduled visits, treatment plan, laboratory tests, lifestyle considerations, and other study procedures.

#### Weight:

4. BMI of 18 to 32 kg/m^2; and a total body weight >50 kg (110 lb).

#### Informed Consent:

5. Capable of giving signed informed consent as described in [Appendix 1](#), which includes compliance with the requirements and restrictions listed in the ICD and in this protocol.

## **5.2. Exclusion Criteria**

Participants are excluded from the study if any of the following criteria apply:

### **Medical Conditions:**

1. Evidence or history of clinically significant hematological, renal, endocrine, pulmonary, gastrointestinal, cardiovascular, hepatic, psychiatric, neurological, or allergic disease (including drug allergies, but excluding untreated, asymptomatic, seasonal allergies at the time of dosing).
2. Positive test result for SARS-CoV-2 infection at the time of Screening or Day -1.
3. History of HIV infection, hepatitis B, or hepatitis C; positive testing for HIV, HBsAg, or HCVA. Hepatitis B vaccination is allowed.
4. Other medical or psychiatric condition including recent (within the past year) or active suicidal ideation/behavior or laboratory abnormality or other conditions or situations related to COVID-19 pandemic (eg, Contact with positive case, residence, or travel to an area with high incidence) that may increase the risk of study participation or, in the investigator's judgment, make the participant inappropriate for the study.
5. History of thrombotic events.

### **Prior/Concomitant Therapy:**

6. Use of prescription or nonprescription drugs and dietary and herbal supplements within 7 days or 5 half-lives (whichever is longer) prior to the first dose of study intervention. (Refer to [Section 6.8](#) Concomitant Therapy for additional details).
7. Systemic therapy with any medications that are strong CYP3A4 inhibitors within 28 days or 5 half-lives (whichever is longer) or strong CYP3A inducers within 28 days or 5 half-lives (whichever is longer) prior to dosing of study intervention
8. Current use of any prohibited concomitant medication(s) or those unwilling/unable to use a permitted concomitant medication(s). Refer to [Section 6.8](#) Concomitant Therapy.

### **Prior/Concurrent Clinical Study Experience:**

9. Previous administration with an investigational drug within 30 days (or as determined by the local requirement) or 5 half-lives preceding the first dose of study intervention used in this study (whichever is longer).

10. Participants who have received a COVID-19 vaccine within the past 2 weeks; and/or participants who are scheduled to receive a second COVID-19 vaccination dose during the in-clinical period of this study.

**Diagnostic Assessments:**

11. A positive urine drug test.
12. Screening supine BP  $>140$  mm Hg (systolic) or  $>90$  mm Hg (diastolic), following at least 5 minutes of supine rest. If BP is  $>140$  mm Hg (systolic) or  $>90$  mm Hg (diastolic), the BP should be repeated 2 more times and the average of the 3 BP values should be used to determine the participant's eligibility.
13. Standard 12-lead ECG that demonstrates clinically relevant abnormalities that may affect participant safety or interpretation of study results (eg, baseline QTcF interval  $>450$  msec, complete LBBB, signs of an acute or indeterminate-age myocardial infarction, ST-T interval changes suggestive of myocardial ischemia, second- or third-degree AV block, or serious bradyarrhythmias or tachyarrhythmias). If the baseline uncorrected QT interval is  $>450$  msec, this interval should be rate-corrected using the Fridericia method and the resulting QTcF should be used for decision making and reporting. If QTcF exceeds 450 msec, or QRS exceeds 120 msec, the ECG should be repeated 2 more times and the average of the 3 QTcF or QRS values should be used to determine the participant's eligibility. Computer-interpreted ECGs should be overread by a physician experienced in reading ECGs before excluding a participant.
14. Participants with ANY of the following abnormalities in clinical laboratory tests at screening, as assessed by the study-specific laboratory and confirmed by a single repeat test, if deemed necessary:
  - AST or ALT level  $\geq 1.0 \times$  ULN;
  - Total bilirubin level  $\geq 1.5 \times$  ULN; participants with a history of Gilbert's syndrome may have direct bilirubin measured and would be eligible for this study provided the direct bilirubin level is  $\leq$  ULN;
  - Estimated glomerular filtration rate (eGFR)  $<70$  mL/min/1.73 m^2 based on the Chronic Kidney Disease Epidemiology Collaboration formula.

